### Planned Study Period

Data will be collected on all patients meeting criteria undergoing emergency surgery on or after the date of UK lockdown due to COVID-19 (23th March 2020) until 22nd May 2020. If sample size is small then the end date for data collection will be extended.

### Study Questions

- 1) Is NLR a predictor of negative outcomes in patients undergoing emergency general surgery?
- 2) Is NLR different in COVID positive versus COVID negative patients undergoing emergency general surgery?

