### Study Title

Peri-Operative Neutrophil:Lymphocyte Ratio (NLR) as a Predictor of Outcomes Following Emergency General Surgery During the COVID-19 Pandemic

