### Primary Outcome

30-day mortality

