### Data Synthesis

For dichotomous outcome measures Relative Risk (RR) will be calculated and significance testing completed using Chi-Squared or Fisher's exact test depending on sample sizes. For continuous variables standardised mean difference (SMD) will be calculated and unpaired, two-tailed student's t-tests used for significance testing.

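### The title and Question 1 ask about prediction, but the planned statistics measure association only, so nothing estimates how well NLR separates deaths from survivors

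*Combined protocol and SAP*

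**What the plan says.** The Study Title presents the marker "as a Predictor of Outcomes Following Emergency General Surgery", and the first item under Study Questions asks "Is NLR a predictor of negative outcomes in patients undergoing emergency general surgery". The Primary Outcome section names "30-day mortality", which is binary.

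Data Synthesis holds the only statistical methods in the document. For binary outcomes, "For dichotomous outcome measures Relative Risk (RR) will be calculated", with "significance testing completed using Chi-Squared or Fisher's exact test depending on sample sizes". For continuous variables, "For continuous variables standardised mean difference (SMD) will be calculated", with an unpaired two-tailed t-test. The section does not name the groups being compared and gives no NLR cut-off.

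The document contains no ROC curve or AUC, sensitivity, specificity, predictive value or prediction model. It states no significance level, and no criterion for when NLR would count as a predictor. Data Collection provides for NLR before or on the day of surgery and on days 1, 2 and 3, with outcomes to 30 days, so the inputs for a discrimination analysis will be available.

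**The concern.** A relative risk compares average risk between groups, and a standardised mean difference compares average values. Both can be clearly non-null while the NLR distributions of patients who die and patients who survive overlap heavily. A question about prediction also needs to know how well the marker ranks or classifies individual patients, and the planned output does not report this.

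The gap is separate from the choice of cut-off, NLR day or covariates. If all of those were settled, the planned output would still be an association measure.

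At stake is the interpretation of the study's first question. The plan can support a statement that NLR is associated with death. It produces no estimate from which a reader could judge NLR as a predictor.

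**Working it through.** The documents give no sample size, mortality, NLR cut-off or significance level, so there is no figure of the plan's own to reproduce. What follows is illustration under stated assumptions.

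**Assumptions.** 30-day mortality m = 0.10; NLR split at the median; two-sided 5% level; equal-variance binormal model for (suitably transformed) NLR. The re-check varied mortality from 5% to 15% and N from 60 to 2000.

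**Step 1: from relative risk to discrimination.**
- Risk in the low group = 2m/(1+RR); risk in the high group = RR × low.
- Sensitivity = 0.5 × high/m; specificity = 0.5 × (1 − low)/(1 − m).
- Implied SMD d = Φ⁻¹(sens) + Φ⁻¹(spec); AUC of continuous NLR = Φ(d/√2).
- AUC of the split itself = (sens + spec)/2.

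| RR | Risk, high v low | Sens | Spec | d | AUC, continuous NLR | AUC, single cut |
|---|---|---|---|---|---|---|
| 2 | 13.3% v 6.7% | 0.67 | 0.52 | 0.43 + 0.05 = 0.48 | 0.63 | 0.59 |
| 3 | 15% v 5% | 0.75 | 0.53 | 0.67 + 0.07 = 0.74 | 0.70 | 0.64 |
| 4 | 16% v 4% | 0.80 | 0.53 | 0.84 + 0.08 = 0.93 | 0.74 | 0.67 |

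The continuous-NLR column is the relevant one. The single-cut value discards the ranking within each half and understates the marker.

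**Step 2: when such relative risks are significant.** Equal halves, deaths in the high v low group:
- 100 patients, 10 deaths: Fisher needs 9 v 1 (RR 9, P = 0.016), AUC 0.84. Uncorrected chi-squared is already below 0.05 at 8 v 2 (RR 4, P = 0.046), AUC 0.74.
- 150 patients, 15 deaths: 12 v 3 (RR 4), Fisher P = 0.027, AUC 0.74.
- 200 patients, 20 deaths: 15 v 5 (RR 3), chi-squared P = 0.018, Fisher P = 0.032, AUC 0.70.
- 300 patients, 30 deaths: 21 v 9 (RR 2.33), Fisher P = 0.033, AUC 0.66.
- 500 patients, 50 deaths: 33 v 17 (RR 1.94), Fisher P = 0.025, AUC 0.63.
- 1000 patients, 100 deaths: 60 v 40 (RR 1.50), Fisher P = 0.045, AUC 0.58.

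So significance goes with progressively weaker discrimination as deaths accumulate. With about 10 deaths it already implies an AUC of roughly 0.74 or more.

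**Step 3: the t-test.** If NLR were compared between deaths and survivors at 10% mortality, the smallest significant SMD would be 0.46 at N = 200 (AUC 0.63), 0.38 at N = 300 (AUC 0.61) and 0.29 at N = 500 (AUC 0.58).

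**Step 4: what the median split does by itself.** With half the patients flagged and 10% dying, a marker that ranked every death above every survivor would still have specificity 0.5/0.9 = 55.6%, PPV 0.10/0.50 = 20% and single-cut AUC (1 + 0.556)/2 = 0.78. Specificities of 52% to 53% in Step 1 therefore say little about NLR.

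**Step 5: precision of an added AUC.** Approximate Hanley-McNeil 95% half-widths at AUC 0.70: ±0.26 with 5 deaths in 100; ±0.13 with 20 in 200; ±0.11 with 30 in 300; ±0.07 with 75 in 500.

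**Step 6: a lower limit above 0.5 is not enough.** AUC 0.58 with 100 deaths in 1000 has SE 0.031 and lower limit 0.58 − 1.96 × 0.031 = 0.519. It excludes 0.5, yet discrimination is weak.

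**The case against.** The best defence is that "predictor" often means no more than a prognostic factor, for which a relative risk is a legitimate measure. The protocol proposes no score, threshold or model, and it plans effect sizes as well as P values. If relative risks are computed for NLR groups, sensitivity, specificity and predictive values follow from the same 2×2 table. An SMD between deaths and survivors could be turned into an AUC.

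Part of this stands: the relative risk is valid as an association, and if association is all that is meant, rewording the title and Question 1 would suffice. But the protocol does not give that narrower meaning, does not plan to report the derived quantities, does not name deaths and survivors as the groups for the SMD, and plans no conversion. A conversion would also rest on normality, and NLR may be skewed.

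Three stronger readings are tempting and are not supported:

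- *A P value below 0.05 will be reported as a yes to Question 1.* The documents state neither a significance level nor a decision rule. This is an inference about how the results would be used.
- *NLR could be called a predictor while barely separating deaths from survivors.* That needs many deaths (Step 2). One centre over about two months, with a possible extension and no stated sample size, does not tell us that there will be many.
- *Specificity near 53%, or 85% of high-NLR patients surviving at RR 3, shows a poor marker.* These figures come mainly from the assumed median split and the base rate (Step 4), and the plan sets no median split.

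**Conclusion.** The point holds as a mismatch between question and analysis: Question 1 and the title concern prediction, and following Data Synthesis exactly yields no estimate of discrimination for 30-day mortality. That rests on the text alone.

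The size is conditional. Under 10% mortality, a median split and an equal-variance binormal model, relative risks of 2 to 3 correspond to an AUC of about 0.63 to 0.70, and such relative risks reach significance from roughly 20 to 50 deaths. With about 10 deaths, significance already implies stronger separation, and the gain from an AUC would then lie mainly in showing how imprecise the estimate is. This is a cheap improvement; it does not invalidate the planned association analysis.

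**What to change.** Add to Data Synthesis:

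- For the NLR time point used for Question 1, the AUC of continuous NLR for 30-day mortality with a 95% CI (DeLong or bootstrap).
- For any cut-off used, sensitivity, specificity, PPV and NPV with 95% CIs, optimism-corrected (for example by bootstrap) if the cut-off is derived from these data.
- A sentence that the relative risk is reported as an association, and that any statement about prediction rests on the size of the AUC and its interval. Neither a significant relative risk nor a lower AUC limit merely above 0.5 should be taken as sufficient (Step 6).

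If only association is intended, reword the title and Question 1 accordingly.

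The cost is a few lines of plan text and code on data already to be collected. The downside is a little extra analysis and a possibly less impressive headline.

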### Primary Outcome

30-day mortality

### Secondary Outcomes

7-day mortality  
Reoperation  
Length of stay  
Post-operative respiratory failure  
Post-operative ARDS  
Post-operative sepsis  
ITU/HDU admission

### Data Collection

Data will be collected using a data extraction template. This will be piloted on 5 included patients and refined as appropriate. Data will be collected from electronic sources including (but not limited to) BlueSpier, EPRO, Cyberlab and Medway. Data will include baseline patient characteristics, operation performed, COVID status and diagnostic method, NLR (pre-operative/day 0 (D0), D1, D2 and D3) and the aforementioned outcome measures. Data will be collected for 30-days following on from the date of surgery.

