### Participants/Study Population

All adult patients (>17 years) undergoing emergency (general) surgery at a single centre (Queens Hospital, Romford, UK) regardless of COVID-19 status will be included. Patients will be organised into those with:

- a) suspected or confirmed COVID-19 (diagnosed clinically, radiologically or with positive viral PCR); and
- b) those for whom COVID-19 was not suspected.

Diagnosis or suspicion of COVID-19 must be made between 7-days before and 30-days after date of surgery in accordance with the COVIDSurg study criteria.

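### One extraction template holds COVID status, NLR and outcomes with no masking or set order, so three secondary outcomes without criteria and clinically judged COVID-19 may be coded with NLR known

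*Combined protocol and SAP*

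**What the plan says.** The study has one instrument: "Data will be collected using a data extraction template". The same section gives its contents as baseline characteristics, the operation, "COVID status and diagnostic method, NLR (pre-operative/day 0 (D0), D1, D2 and D3) and the aforementioned outcome measures", all taken from electronic hospital sources. It adds a pilot: "This will be piloted on 5 included patients and refined as appropriate". It does not mention masking the extractor, a second extractor, or an order in which fields are completed.

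The items to be coded differ in how much judgement they need:

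- The primary outcome is "30-day mortality".
- Among the seven secondary outcomes, 7-day mortality, reoperation, length of stay and ITU/HDU admission are recorded events.
- The other three, "Post-operative respiratory failure", ARDS and sepsis, are listed by name only, with no diagnostic criteria.
- Under Participants/Study Population, the COVID-19 group is "suspected or confirmed COVID-19 (diagnosed clinically, radiologically or with positive viral PCR"). The diagnosis or suspicion must arise between 7 days before and 30 days after surgery, with a reference to an external cohort study's criteria.

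On timing, the surgery window is given as "23th March 2020) until 22 nd May 2020. If sample size is small then the end date for data collection will be extended", and the anticipated start date is 25 May 2020. On follow-up: "Data will be collected for 30-days following on from the date of surgery".

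**The concern.** NLR is the predictor in Question 1 and the compared variable in Question 2. If the person who decides from the notes whether a patient had sepsis, or was suspected of COVID-19, already knows the NLR, borderline records may be resolved differently at high and low NLR. That is differential misclassification. For Question 1 it could add events among high-NLR patients. For Question 2 it could move high-NLR patients into the COVID-19 group. If an extractor expects NLR to track bad outcomes and infection, both errors lean towards a positive answer.

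The relative risks, standardised mean differences and tests in the Data Synthesis section cannot detect or correct such an error, and a larger sample does not dilute it. It has to be prevented at extraction.

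**Working it through.** The plan states no sample size, event rate or effect size, so there is no figure to reproduce. Two things can be checked: whether NLR precedes coding, and how large an error could follow.

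**1. Is NLR on record before extraction starts?** The inputs are the dates in Planned Study Period, Anticipated Start Date and Data Collection.

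- Surgery dates from 23 March to 22 May: 9 (March) + 30 (April) + 22 (May) = 61.
- Day 3 for the last planned date: 22 May + 3 days = 25 May, the start date. Day 3 has therefore been reached for all 61 dates.
- Thirty-day follow-up is complete by 25 May for surgery on or before 25 April: 9 + 25 = 34 dates.
- Follow-up is still running for surgery from 26 April to 22 May: 61 − 34 = 27 dates (27/61 = 44%). The last ends on 21 June 2020, before any extension of the window.

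Extraction therefore follows NLR for every planned date, although outcomes are not all in the past. COVID-19 suspicion may arise up to day 30, so that classification can also come after day 3 NLR is known.

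**2. Which coded items leave room for judgement?** Of eight outcomes (one primary, seven secondary), three lack criteria and depend on reading notes. The COVID-19 grouping has named diagnostic routes and a time window, but the document itself gives no rule for reading clinical suspicion from the notes.

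**3. How large could the error be?** All rates below are assumptions, not document figures. Let the true risk be *p* in both NLR groups, so the true RR is 1.00.

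*Version A.* An extra *e* of **all** high-NLR patients are coded as events: RR = (*p* + *e*)/*p*. With *p* = 0.15:

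- *e* = 0.02: 0.17/0.15 = 1.13
- *e* = 0.05: 0.20/0.15 = 1.33
- *e* = 0.10: 0.25/0.15 = 1.67

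*Version B.* A share *u* of high-NLR **non-cases** is upgraded: RR = (*p* + *u*(1 − *p*))/*p*.

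- *p* = 0.10: *u* = 0.02 gives 0.118/0.10 = 1.18; *u* = 0.10 gives 0.190/0.10 = 1.90
- *p* = 0.20: *u* = 0.02 gives 0.216/0.20 = 1.08; *u* = 0.10 gives 0.280/0.20 = 1.40

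*Version C.* Only a borderline fraction *b* can be upgraded: RR = (*p* + *b·e*)/*p*, so the excess over 1 shrinks in proportion to *b*. With *p* = 0.15 and *b* = 0.20 (assumed):

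- *e* = 0.02: 0.154/0.15 = 1.03
- *e* = 0.10: 0.170/0.15 = 1.13

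If the extractor's judgement does not depend on NLR (*e* = *u* = 0), the expected RR is 1.00. No comparable figure can be given for Question 2, because the documents give neither the spread of NLR nor the share of patients classed on clinical grounds.

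**The case against.** The strongest reply is that the documents are silent rather than wrong. The list of contents is prose, not the form, and it does not fix the order of fields. Read as an order, it would put COVID status before NLR. A reader might infer that extractors do look at NLR when coding; the documents do not say so. What stands is that nothing prevents it.

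Other parts of the reply also stand:

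- A reader might infer that COVID-19 has no definition. It has three diagnostic routes, a time window and an external reference whose content cannot be judged here. The method of diagnosis is recorded, so a PCR-only comparison is possible, though none is planned. The gap is limited to clinical diagnosis or suspicion.
- A reader might infer that the study is wholly retrospective. That is true of NLR, but 30-day follow-up is still running for 27 of 61 surgery dates at the start. This does not weaken the point, since those outcomes too would be coded after NLR is known.
- The mechanism speaks of high NLR, but the plan sets no cut-off or NLR groups. The direction of bias is plausible, not demonstrated.
- Treating clinicians may have had the blood count when they recorded sepsis or suspicion. No order of extraction can undo that.
- The plan does not say that the five pilot patients will be extracted again after refinement. No effect on results has been shown; this is housekeeping.

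It can also be said that the basic gap is missing definitions, with masking a preference on top. Criteria would narrow the room for judgement but would not remove it, and setting an order is a small addition.

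**Conclusion.** The point holds as an unguarded risk of limited reach, and the change is desirable rather than essential. Every planned day 0 to day 3 NLR exists by the start, and the plan has neither masking nor an extraction order. Three of eight outcomes and the clinically judged part of the COVID-19 grouping may therefore be coded with NLR known. That could bias Question 1 for those three outcomes, and Question 2, towards a positive answer.

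The size is illustrative only. The range of 1.13 to 1.67 assumes a true risk of 15% and 2 to 10 extra events per 100 of all high-NLR patients. Other assumed inputs in the working give values from 1.03 to 1.90.

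A reader might infer that the primary result is compromised. The documents do not support that: 30-day mortality is a recorded event that leaves the extractor little to judge, as are 7-day mortality, reoperation, length of stay and ITU/HDU admission.

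**What to change.** Amend the Data Collection section so that extraction runs in a fixed order, with the same extractors and sources:

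1. After the five-patient pilot, fix written criteria, chosen by the investigators, for respiratory failure, ARDS, sepsis and clinically diagnosed or suspected COVID-19.
2. Code COVID status (with date and method) and the judged outcomes to those criteria. Lock these fields once each patient's 30 days are complete.
3. Only then pull neutrophil and lymphocyte counts from the laboratory system and merge them by study number.

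It would be tidy to code the five pilot patients again on the final forms.

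**Cost.** No new data source is needed, but each record is handled twice. The documents give no staffing or workload, so the effort cannot be priced; it is probably small, but not nil. The blood counts for the last planned patients would wait until their follow-up ends on 21 June 2020, when their outcomes become complete in any case.

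**Limits to state in the protocol.** Masking is incomplete where blood results appear in the clinical notes. The order removes only the extractor's contribution, not any influence of the blood count on what treating clinicians recorded.

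### The plan does not require NLR on days 1–3 to precede the five non-fatal outcomes it is meant to predict, and names no primary NLR time point for 30-day mortality

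*Combined protocol and SAP*

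**What the plan says.** All references are to the combined protocol and SAP.

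- **Study Questions.** The first question is predictive: "Is NLR a predictor of negative outcomes in patients undergoing emergency general surgery". The Study Title also calls NLR a predictor.
- **Primary Outcome.** "30-day mortality".
- **Secondary Outcomes.** Seven are listed. Five are non-fatal events: reoperation, respiratory failure, ARDS, "Post-operative sepsis" and "ITU/HDU admission". The other two are 7-day mortality and "Length of stay". None of the five events has an onset date or a time window of its own.
- **Data Collection.** The template takes "NLR (pre-operative/day 0 (D0), D1, D2 and D3) and the aforementioned outcome measures". On follow-up: "Data will be collected for 30-days following on from the date of surgery". Values come from existing electronic records. The template is to be piloted on five patients and then refined.
- **Data Synthesis.** This is the whole analysis plan. It says "For dichotomous outcome measures Relative Risk (RR) will be calculated and significance testing completed using Chi-Squared" or Fisher's exact test, and it gives SMDs with two-tailed t-tests for continuous variables. It does not mention NLR time points.

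No section names a primary NLR time point, requires the sample to precede the event, or asks for event onset dates.

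**The concern.** A predictor has to be measured before the outcome. Here the outcome window opens at surgery and three of the four NLR values fall inside it. If sepsis begins on day 1, the day-3 NLR of that patient partly measures the response to sepsis. Comparing day-3 NLR between patients with and without sepsis would then show a difference even if NLR carried no advance information, and study question 1 could be answered wrongly for these outcomes.

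The primary outcome has a different problem. A blood sample cannot follow death, so the order is safe. But four NLR values are available and none is designated, so the one reported as answering study question 1 could be chosen once the results are known.

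**Working it through.** The plan states no sample size, power, alpha or event count, so there is no figure of its own to reproduce. The first step needs only the text. The others are illustrations on assumed inputs.

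**1. Order of sample and event, from the text**

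| Outcome | Can it precede a day 1–3 sample? | Ordering rule in the plan |
|---|---|---|
| Reoperation, respiratory failure, ARDS, sepsis, ITU/HDU admission | Yes | None |
| 7-day and 30-day mortality | No | Not needed |
| Length of stay | It is a duration, not an event; later values may be missing after discharge | Not applicable |

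**2. Effect of ignoring the order**

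Assumptions: NLR on a scale where it is normal with SD 1; event proportion p = 0.2; n = 100 or 200; two-sided alpha 0.05; NLR unrelated to future events. A share f of events precedes the day-3 sample, and each raises NLR by d SD. I use the t-test because the RR needs an NLR cut-off, which the plan does not give.

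Apparent SMD = f·d / √[p(1 + f(1−f)d²) + (1−p)]. For f = 0.5 and d = 1.0 this is 0.5 / √(0.2 × 1.25 + 0.8) = 0.5 / √1.05 = 0.488.

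| f | d | Apparent SMD | p<0.05, n=100 | p<0.05, n=200 |
|---|---|---|---|---|
| 0.10 | 0.5 | 0.050 | 5.3% | 6.0% |
| 0.10 | 1.0 | 0.099 | 7.4% | 8.9% |
| 0.25 | 0.5 | 0.124 | 8.2% | 11.4% |
| 0.25 | 1.0 | 0.245 | 18.1% | 29.2% |
| 0.50 | 0.5 | 0.248 | 16.7% | 28.1% |
| 0.50 | 1.0 | 0.488 | 49.5% | 76.5% |

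The rejection rates are simulated (20,000 replicates per cell for f = 0.10, 10,000 for the rest). Restricting to patients event-free at sampling and counting only later events gives 4.5–5.5% throughout.

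**3. Free choice among four time points for 30-day mortality**

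With no true association and four two-sided 0.05 tests on correlated normal statistics, the chance of at least one p<0.05 is 14.4%, 11.5% and 9.3% at between-day correlations of 0.6, 0.8 and 0.9. Independence would give 1 − 0.95⁴ = 18.5%, but repeated values in the same patients are not plausibly independent.

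**4. What landmarking costs**

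If half the events precede the sample, 10 of 20 events remain at n = 100 and 20 of 40 at n = 200. T-test power for a true SMD of 0.5 falls from 51% (20 v 80) to 31% (10 v 80), and from 80% (40 v 160) to 55% (20 v 160).

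**The case against.** **The plan permits the misuse but does not prescribe it.** Data Collection is a list of variables. Data Synthesis never says that every NLR value will be tested against every outcome, or that the most favourable will be reported; reporting all four would not be selective. This is right. The point is therefore an unfilled gap, not an error that must occur. A reader might multiply four time points by eight outcomes into a family of 32 tests, but the documents define no such family.

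**The size depends on chosen inputs.** This also stands. If few events precede the sample and the rise is small, the false-positive rate is close to nominal. The documents give nothing from which to estimate event timing.

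**Mortality and length of stay.** A reader might infer that day 1–3 NLR is also biased for mortality because only survivors are sampled. The documents do not support this as a defect in the planned test. Everyone sampled on a given day is alive, so every death counted is a later one, and landmarking leaves that analysis set unchanged. Replacing length of stay with residual stay does not help either. If stay runs from surgery, residual stay subtracts the same number of days from everyone sampled that day, so the SMD and t-test are identical. It also does not recover patients already discharged. What remains is a matter of interpretation: the patients with a value may differ from day to day.

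**Some protection exists.** Sepsis, ARDS and respiratory failure are labelled post-operative, and the D0–D3 labels already give the sample day. But a post-operative label does not place onset after a day 1–3 sample, and onset dates are not requested.

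**Repeated NLR may be meant descriptively.** Then the plan should say so, because the title and first study question speak of prediction.

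**Conclusion.** The concern holds in two parts. For the five non-fatal events, the plan allows an NLR measured after the event to be counted as predicting it. For 30-day mortality the order is not at fault, but the NLR time point that answers the primary question is open.

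Confidence in the gap is high, because it rests on the text alone. The size is illustrative. Under the inputs above, a non-predictive day-3 NLR gives p<0.05 in about 5–9% of studies when 10% of events precede the sample and about 8–77% when 25–50% do, against about 5% with landmarking. Choosing among four correlated time points gives about 9–14% for mortality.

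This should be changed, but it is not a fatal flaw: the ordering problem does not touch the primary outcome, and the remedy is cheap.

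**What to change.** 1. Add onset dates for the five non-fatal events to the extraction template; the planned pilot and refinement is the occasion. For days 1, 2 and 3, analyse only patients sampled that day and free of the outcome at sampling, and count only later events.
2. Pre-specify one NLR time point against 30-day mortality as the primary analysis and label the others exploratory. The last value before incision is a natural choice for a prediction claim, but another single pre-specified time point would also do. If a pre-operative value is chosen, state that D0 means before incision. It would cover only part of the peri-operative question in the title.
3. Report the number of patients with an NLR value each day, because day 1–3 values exist only for patients alive, in hospital and sampled.

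**Cost.** Some wording and slightly more extraction, with the dates expected to be in the same records. The day 1–3 analyses will have fewer patients and events, with the loss of power shown above if half the events come first. ITU/HDU admission loses most if many patients are admitted directly after surgery.
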